I will not initiate this study without approval from the Institutional Review Board (IRB)/Research Ethics Board (REB)/Independent Ethics Committee (IEC) and I understand that any changes in the protocol must be approved in writing by Aldeyra Therapeutics, Inc., and the Institutional Review Board/Ethics Committee before they can be implemented, except when necessary to eliminate immediate hazards to the subjects.

I will use only the informed consent form approved by Aldeyra Therapeutics and by my IRB/REB/IEC and will fulfill all responsibilities for submitting pertinent information to the IRB/REB/IEC responsible for this study.

By my signature below, I attest that I have read, understand, and agree to abide by all the conditions, instructions, and restrictions contained in Protocol Number ADX-102-SLS-006, and will conduct the trial in accordance with the International Council for Harmonisation (ICH) guidelines on Good Clinical Practice (GCP) and applicable regulatory requirements.

Site Name

Site Address

Investigator's Printed Name

Investigator's Signature

Date

SYNOPSIS

Name of Sponsor Company:		Drug Under Study:			
Aldeyra Therapeutics, Inc.		ADX-102			
Title of Protocol: A Phase 3 Rand Evaluate the Safety and Efficacy Sjögren-Larsson Syndrome (SLS)	lomized, Double-Blind, V / of ADX-102 1% Top	ehicle-Controlled, Parallel Group Trial to bical Dermal Cream in Subjects with			
Protocol Number:	Phase: 3	Indication: Sjögren-Larsson Syndrome;			
ADX-102-SLS-006		Dermatological Signs and Symptoms			
Subject Population: Subjects 3 years and active ichthyosis.	ears of age and older wit	h genetically-confirmed diagnosis of SLS			
Number of Subjects:					
Part 1: Approximately 9 subjects					
Part 2: Approximately 30 subjects, to	be confirmed in Part 1				
Number of Centers:					
Approximately 8 centers globally					
Test Products / Doses / Mode of A	dministration:				
ADX-102 1% drug product is formula	ited as a topical dermal cr	eam.			
ADX-102 or vehicle topical dermal cre each application administered appro- percent body surface area (BSA) une	eam will be applied once o eximately 24 hours apart. der treatment will be mea	laily to the designated treatment area with A standard amount of study drug for the sured for application.			
Primary Objective: To evaluate th ichthyosis associated with SLS.	ne efficacy of ADX-102 1	% topical dermal cream for treatment of			
Secondary Objectives: To evaluat topical dermal cream in subjects with	ate the safety and secon n SLS.	dary efficacy endpoints of ADX-102 1%			
Study Endpoints					
Primary Endpoint:					
The primary efficacy endpoint is the assessed by the Investigator in the ta	Visual Index for Ichthyosis arget efficacy area.	s Severity (VIIS) scaling severity score as			

Study Design:

This is a two-part, randomized, double-blind, vehicle-controlled, parallel-group Phase 3 clinical trial with an initial assessment of increasing BSA treatment (Part 1). After the completion of Part 1, a separate set of eligible subjects will be enrolled to assess all areas affected by ichthyosis (Part 2).

Part 1 Design:

Part 1 will evaluate the safety, tolerability, and efficacy of treatment to the affected area of ichthyosis

Qualified subjects will be randomized in a 2:1 ratio to receive ADX-102 1% or vehicle. Subjects or caregivers will apply study drug (i.e., ADX-102 1% or vehicle) once daily to a treatment area identified by the Investigator from Week 1 through Week 12. If the Investigator determines that there are no safety or tolerability issues at the end of Week 12, treatment will increase to all of the affected areas of ichthyosis on one-half of the body from Week 13 through Week 20. If no safety or tolerability issues are identified at the end of Week 20 the treatment will increase to all affected areas of ichthyosis on the entire body from Week 24.

Subjects completing 24 weeks of study drug treatment will then be monitored for an additional 4 weeks for safety.

In total, subjects will be followed for up to 28 weeks and monitored for safety and efficacy at up to 10 study visits: up to 6 site visits and 4 home visits. Apart from the Day 1 and Day 2 visits, each study visit has a \pm 5-day window, and home visits have a \pm 3-day window.

Study procedures are outlined in the Schedule of Assessments (Table 1 and Table 1-1).

Subjects who are randomized in Part 1 will not be eligible to participate in Part 2.

Part 2 Design:

Part 2 will evaluate the safety, tolerability, and efficacy of treatment to the affected area of ichthyosis on the body (approximately 80-90% BSA in a typical SLS patient) over 24 weeks of exposure.

Qualified subjects will be randomized in a 2:1 ratio to receive either ADX-102 1% or vehicle. The appropriate sample size for Part 2 will be confirmed in Part 1. Subjects will be followed for up to 28 weeks and monitored for safety and efficacy at up to 10 study visits: up to 7 clinic visits and 3 telephone calls with the site. Apart from the Day 1 and Day 2 visits, each study visit has a \pm 5-day window, and telephone calls have a \pm 3-day window.

Study procedures are outlined in the Schedule of Assessments (Table 2 and Table 2-1).

Subjects who complete Part 1 or Part 2 of the study will be eligible to continue into a separate open-label extension study.

Criteria for Inclusion:

Subjects meeting all the following criteria will be considered eligible for study entry:

- 1. Subject is aged 3 years or older.
- 2. Subject has a genetically-confirmed diagnosis of SLS.
- 3. Subject has active ichthyosis that is Grade 2 or higher on the VIIS scaling severity score.
- Subject or subject's caretaker is willing and able to provide written informed consent prior to the initiation of any study procedures. Assent will be solicited from pediatric subjects capable of providing assent.
- 5. Females of child-bearing potential: Negative pregnancy test at Screening and Baseline Visits.
- 6. Subjects who are sexually active agree to use medically acceptable method (as defined by the Investigator) of birth control as follows:
 - For females: Compliant with a contraceptive regimen during the study if of child-bearing potential or documented to be surgically sterile or post-menopausal.
 - For males: Compliant with a contraceptive regimen during the study or documented to be surgically sterile.

Criteria for Exclusion:

Subjects meeting any of the following criteria will be excluded from the study:

- 1. Subject has evidence of a serious active infection.
- 2. Systemic or topical retinoids or other topical medications, not including emollients, within the past 30 days Baseline Visit 1.
- 3. Subject has received an investigational systemic or topically administered drug within the past 30 days prior to Baseline Visit 1.
- 4. Subject is currently taking and was unwilling or unable to discontinue any medication excluded in Section 5.7.1.
- 5. Subject is currently receiving immunosuppressive therapy, including intermittent or low-dose systemic corticosteroids.
- 6. Subject has a known allergic reaction to any ingredients of study drug formulation.
- 7. Subject has a history of any malignancy.
- 8. Subject is known to be human immunodeficiency virus positive or had other known immunodeficiency.
- 9. Subject has any clinically significant laboratory test abnormalities or a history of any other condition that, in the opinion of the Investigator, could compromise the subject's ability to comply with the protocol or that could compromise the subject's safety or the interpretation of the study results.
- 10. Subject is currently participating in any other therapeutic clinical study.
- 11. Subject is pregnant or lactating.

Statistical Analysis:

Part 1 and Part 2 will be analyzed in a similar fashion with the exception that the Part 1 analysis will include a sample size evaluation. Part 1 analyses in some instances may be confined to the descriptive aspect of the evaluation (i.e., inferential p-values may be omitted) due to the small sample size of 6 treated and 3 control patients.

The primary efficacy endpoint (VIIS scaling severity as assessed by the Investigator in the target efficacy area) as well as all secondary efficacy variables that are captured on a continuous or semi-continuous

scale

will be expressed as baseline to ending change scores. Two-sided 95% confidence intervals (CIs) will be computed and used descriptively for all variables but also to evaluate change relative to a standard for some variables (i.e., by determining whether the CI includes or excludes the standard).

The two-sided 95% CI for VIIS scaling severity will be used to evaluate the primary endpoint as follows. An efficacy claim from Part 2 will be made if: 1) the lower confidence interval is above zero, 2) the midpoint of the confidence interval is at least 0.5 units is size, and 3) at least 50% of subjects have favorable change scores of one or greater.

Response over time will be converted to one or more Area Under the Curve parameters and evaluated using a generalized linear model. VIIS outcome scores and other continuous or semi-continuous outcome variables will be evaluated using a Mixed Model Repeated Measures (MMRM) analysis. Conversion of VIIS or other scales to indicate response (yes/no) will occur (e.g., 0.5 VIIS improvement, 1 unit VIIS improvement) and be evaluated as secondary endpoints. Logistic or Generalized Estimating Equation (GEE) modeling will be used to evaluate incidence of response overall and/or by time. Time to Event analysis (e.g., Kaplan-Meier with log rank test, proportional hazards [PH] modeling) will be used to evaluate time to response.

To increase statistical power, covariates may be incorporated into the computation of 95% confidence intervals (e.g., through the use of a mean centered covariate in a regression model to predict the mean pre-treatment to post-treatment difference) and/or into logistic, GEE, PH, MMRM and generalized linear models.

All analyses will be specified *a priori* in an Statistical Analysis Plan (SAP) to be completed prior to database lock for Part 1. The SAP will serve as the summative and definitive plan of analysis. Analyses not described in the SAP will be labeled as *post-hoc*. The SAP will outline all analyses that will be performed in Part 1 and in Part 2 of this study.

Sample Size Rationale:

Part 1 will assess the effect size on the VIIS scaling severity score, and will confirm the sample size needed for Part 2. Part 2 is expected to require approximately 30 subjects.

Data Safety Monitoring Board:

An independent data safety monitoring board (DSMB) will be established to review all available safety data after approximately 9 subjects have completed Week 24 in Part 1. The assessment of safety will be determined from dermatological endpoints, vital sign measurements, physical examinations, hematology and chemistry laboratory testing, ECG readings, use of concomitant medications, and review of AEs. Based on the safety data provided, the DSMB will provide recommendations about stopping or continuing the trial.

The DSMB will be advisory to the Sponsor's clinical trial leadership group Steering Committee which will be blinded during Part 1 until database lock. The Steering Committee will be responsible for promptly reviewing the DSMB recommendations, to decide whether to continue or terminate the trial, and to determine whether amendments to the protocol or changes in study conduct are required.

Additional DSMB reviews will occur approximately every 6 months throughout the trial, or as deemed necessary by the DSMB or Sponsor to ensure subject safety and well-being. Study enrollment and dosing will continue while the DSMB evaluates data. A DSMB charter will be prepared. The charter will contain the required information for the formation, activities, and conduct of the DSMB.

Table 1. Part 1 Schedule of Events and Assessments

	Screening ¹	Baseline Visit 1	Visit 2	Visit 3	Visit 4	Visit 5	Visit 6	Visit 7	ET Visit 8 ²	Safety Follow-Up Visit 9
	Day -7 to -1	Week 1 Day 1	Week 1 Day 2	Week 4 ± 3 days	Week 8 ± 3 days	Week 12 ± 5 days	Week 16 ± 3 days	Week 20 ± 5 days	Week 24 ± 5 days	Week 28 ± 3 days
Evaluation	Site Visit	Site Visit	Site Visit	Home Visit	Home Visit	Site Visit	Home Visit	Site Visit	Site Visit	Home Visit
Informed consent / assent	х									
Eligibility review	х	Х								
Demographics / medical history	Х									
Concomitant medications	х	Х	Х	х	Х	х	Х	Х	Х	Х
Adverse events	х	Х	Х	х	Х	х	Х	Х	Х	Х
Urinalysis / pregnancy test ³	х	Х				х		х	х	
12-Lead ECG (see Table 1-1)	Х	Х				х		х	Х	
Vital Signs (see Table 1-1)	Х	Х	х			Х		Х	х	
Physical exam ⁴	х	Х	х			х		х	х	
Dermatologic exam	Х	Х	Х	Х	Х	Х	Х	Х	Х	Х
Digital photography⁵		Х		X ₆	X6	х	X ⁶	х	х	X ⁶
VIIS (Investigator-assessed)		Х	Х			Х		Х	Х	
Global impression of severity		Х				х		х	х	
Patient/Observer-reported scales7		Х				Х		Х	х	
PD sample collection ⁸		Х	х			х		х	х	
Clinical laboratory testing ⁹	х	Х				х		х	х	
PK sample collection ¹⁰ (see Table 1-1)		Х	х			х		х	х	
Randomization		Х								
Administer study drug		X ¹¹	Х	х	х	X ¹¹	Х	X ¹¹		
Dispense study drug & diary			Х			Х		Х		
Collect study drug & diary						Х		Х	Х	

ET = early termination; ECG = electrocardiogram; PD = pharmacodynamic; PK = pharmacokinetic; VIIS = Visual Index for Ichthyosis Severity

1. Samples collected for urinalysis and clinical laboratory tests may be analyzed at a local lab.

2. Subjects who terminate early from the study will undergo, if possible, all of the assessments and procedures scheduled for Visit 8 (Week 24).

3. Urine pregnancy test for female subjects of child-bearing potential only. Test can be analyzed at the study site.

4. Complete physical exam, including height and weight collection, performed at Screening Visit only; symptom directed physical exams at all other timepoints.

- 5. Subjects should refrain from bathing and applying study drug or as-needed topical symptom control therapy (emollients) to the treatment area within 12 hours of obtaining digital photographs.
- 6. During at-home visits, photographs will only be taken if there are any safety concerns.
- 7. Patient/Observer-reported scales to be administered: EQ-5D-5L, global impression of severity, global impression of bother, global impression of treatment, itching, scratching, burden of bathing/showering, and Children's Dermatology Life Quality Index (CDLQI) / Dermatology Life Quality Index (DLQI).
- 8. PD assessments include skin cell samples and transepidermal water loss (TEWL) procedures.
- 9. Clinical laboratory includes hematology and chemistry. Refer to Sections 6.15.1.1 and 6.15.1.2 for more detail.
- 10. PK collection include blood and urine samples.
- 11. Study drug will be administered daily. At study visits when PK samples are collected, study drug may be administered at the study clinic after pre-dose PK samples have been obtained. At Visit 1, Investigator should apply study drug to the initial treatment area (~20% BSA) during the visit. At Visit 2, study drug may be applied to the initial treatment area during the visit (after pre-dose PK sample collection) by the Investigator or subject/caregiver. At Visit 5, if the treatment area is expanded to up to 45% BSA, the Investigator should apply study drug to the treatment area. At Visit 7, if the treatment area is expanded to up to 90% BSA, Investigator should apply study drug to the treatment area.

Visit		Visit 1				Visit 2	Visits 5, 7 and 8				
Time (hours)	Pre-Dose	1	2	4	8	24	Pre-Dose	1	2	4	8
Window	-	± 15 min	± 15 min	± 15 min	± 15 min	± 60 min	-	± 15 min	± 15 min	± 15 min	± 15 min
Adults (age ≥ 12 years old)											
12-Lead ECG	Х	Х	Х	Х	Х		Х	Х	Х	Х	Х
Vital Signs	х	Х	Х	Х	Х	Х	х	Х	Х	Х	Х
Blood PK Samples	Х	Х	Х	Х	Х	Х	Х	Х	Х	Х	Х
Urine PK Samples	Х				Х		Х				Х
Children (age < 12 years old)											
12-Lead ECG	Х	Х		Х			Х	Х		Х	
Vital Signs	Х	Х		Х		Х	Х	Х		Х	
Blood PK Samples	Х	Х		Х		Х	Х	Х		Х	
Urine PK Samples	Х			Х			Х			Х	

Table 1-1. Part 1 Pharmacokinetic and Cardiac Monitoring

Table 2. Part 2 Schedule of Events and Assessments

	Screening ¹	Baseline Visit 1 ¹	Visit 2	Visit 3	Visit 4	Visit 5	Visit 6	Visit 7	ET Visit 8 ²	Safety Follow-up Visit 9
	Day -7 to -1	Week 1 Day 1	Week 1 Day 2	Week 4 ± 3 days	Week 8 ± 5 days	Week 12 ± 3 days	Week 16 ± 5 days	Week 20 ± 3 days	Week 24 ± 5 days	Week 28 ± 5 days
Evaluation	Site Visit	Site Visit	Site Visit	Telephone	Site Visit	Telephone	Site Visit	Telephone	Site Visit	Site Visit
Informed consent / assent	Х									
Eligibility review	Х	Х								
Demographics / medical history	Х									
Concomitant medications	Х	Х	Х	Х	Х	Х	Х	Х	Х	X
Adverse events	Х	Х	Х	Х	х	х	х	х	Х	x
Urinalysis / pregnancy test ³	Х	Х			Х		Х		Х	
12-Lead ECG (see Table 1-1)	Х	Х			Х				Х	
Holter Monitoring		Х			Х				Х	
Vital Signs (see Table 1-1)	х	Х	Х		Х		Х		х	
Physical exam ⁴	Х	Х	Х		Х		х		Х	
Dermatologic exam	х	Х	Х		Х		Х		х	Х
Digital photography⁵		Х			Х		х		Х	Х
VIIS (Investigator-assessed)		X ⁶	Х		х		х		Х	Х
Global impression of severity		Х			Х		х		Х	Х
Patient/Observer-reported scales ⁷		Х			Х		Х		х	х
PD sample collection ⁸		Х	Х		Х		Х		х	
Clinical laboratory testing ⁹	х	Х			Х		Х		х	
PK sample collection ¹⁰ (see Table 1-1)		Х	Х		Х		Х		Х	
Randomization		Х								
Administer study drug ¹¹		Х	Х	Х	Х	Х	Х	Х		
Dispense study drug & diary			Х		Х		Х			
Collect study drug & diary					Х		Х		Х	
Exit interview									X ¹²	

ECG = electrocardiogram; ET = early termination; PD = pharmacodynamic; PK = pharmacokinetic; VIIS = Visual Index for Ichthyosis Severity

1. Samples collected for urinalysis and clinical laboratory tests may be analyzed at a local lab.

- 2. Subjects who terminate early from the study will undergo, if possible, all of the assessments and procedures scheduled for Visit 8 (Week 24).
- 3. Urine pregnancy test for female subjects of child-bearing potential only. Tests can be analyzed at the study site.
- 4. Complete physical exam, including height and weight collection, performed at Screening Visit only; symptom directed physical exams at all other timepoints.
- 5. Subjects should refrain from bathing and applying study drug or as-needed topical symptom control therapy (emollients) to the treatment area within 12 hours of obtaining digital photographs.
- 6. VIIS must be independently assessed by two different Investigators at Baseline Visit 1 only.
- 7. Patient-/caregiver-reported scales to be administered: EQ-5D-5L, global impression of severity, global impression of bother, global impression of treatment, itching, scratching, burden of bathing/showering, and Children's Dermatology Life Quality Index (CDLQI) / Dermatology Life Quality Index (DLQI).
- 8. PD assessments include skin cell samples and transepidermal water loss (TEWL) procedures.
- 9. Clinical laboratory includes hematology and chemistry. Refer to Sections 6.15.1.1 and 6.15.1.2 for more details.
- 10. PK sample collection (blood and urine) from approximately 16 subjects.
- 11. Study drug will be administered daily. At study visits when PK samples are collected, study drug may be administered at the study site after pre-dose PK samples have been obtained.
- 12. Exit interviews should be conducted within 30 days of Visit 8.

Visit			V	isit 1			Visit 2			Visit	s 4 and 8			Visit 6
Time (hours)	Pre- Dose	1	2	4	8	12	24	Pre- Dose	1	2	4	8	12	Pre- Dose
Window	-	± 15 min	± 60 min	-	± 15 min	± 15 min	± 15 min	± 15 min	± 15 min	-				
Adults (age ≥12 yea	ars old)													
12-Lead ECG	Х	Х	Х	Х	Х	Х		Х	Х	Х	Х	Х	Х	
Vital Signs	Х	Х	Х	Х	Х	Х	Х	Х	Х	Х	Х	Х	Х	Х
Blood PK Samples	Х	Х	Х	Х	Х	Х	Х	Х	Х	Х	Х	Х	Х	Х
Urine PK Samples	Х				Х			Х				Х		
Children (age < 12	years old	d)												
12-Lead ECG	Х	Х		Х				Х	Х		Х			
Vital Signs	Х	Х		Х			Х	Х	Х		Х			Х
Blood PK Samples	Х	Х		Х			Х	Х	Х		Х			Х
Urine PK Samples	Х			Х				Х			Х			

Table 2-1. Part 2 Pharmacokinetic and Cardiac Monitoring

TABLE OF CONTENTS

IN	VESTIC	SATC	R STATEMENT	2
SY	'NOPSI	S		3
ΤA	BLE OI	F CO	NTENTS	11
LIS	ST OF 1	ΓABL	ES	15
LIS	ST OF A	\BBF	REVIATIONS AND DEFINITION OF TERMS	16
1		IN	IRODUCTION	18
	1.1	Sjö	gren-Larsson Syndrome	18
	1.2	Th	erapeutic Rationale for ADX-102 in Sjögren-Larsson Syndrome	18
	1.3	Cli	nical Trials of ADX-102	19
	1.3	3.1	Sjögren-Larsson Syndrome	19
	1.3	3.2	Ocular Indications	20
	1.4	Mir	nimization of Risk	20
	1.5	Po	tential Benefit	20
	1.6	Ra	tionale for Dose Selection	21
2		ST	UDY OBJECTIVES AND ENDPOINTS	21
	2.1	Stu	udy Objectives	21
	2.1	1.1	Primary Objective	21
	2.1	1.2	Secondary Objective	21
	2.2	Stu	udy Endpoints	21
	2.2	2.1	Primary Endpoint	21
	2.2	2.2	Secondary Endpoints	21
3		IN	/ESTIGATIONAL PLAN	22
	3.1	Ov	erall Study Design and Plan	22
	3.2	As	signing Subjects to Treatment Groups	23
	3.2	2.1	Subject Numbering	23
	3.2	2.2	Randomization	23
	3.3	Bli	nding and Unblinding	23
	3.3	3.1	Blinding	23
	3.3	3.2	Emergency Unblinding	23
	3.4	Sa	fety Oversight	24

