7.7 Visit 7 (Week 20 ± 5 days) – Site Visit

- Collect Patient/Observer-reported scales (Section 6.11)
- Collect study drug supply and diary (Sections 6.18.1 and 6.18.2)
- Record concomitant medications and adverse events (Sections 6.4 and 6.5)
- Collect urine sample for urinalysis and pregnancy test, if applicable (Sections 6.15.1.3 and 6.15.1.4)
- 12-lead ECG (Section 6.6)
- Collect vital signs (Section 6.7)
- Symptom-directed physical exam (Section 6.8)
- Complete dermatologic examination (Section 6.12)
- Take digital photography (Section 6.13)
- Complete VIIS (Section 6.9)
- Complete Global Impression of Severity (Section 6.10)
- PD sample collection (Section 6.14)
- Collect blood samples for hematology and chemistry (Sections 6.15.1.1 and 6.15.1.2)
- PK sample collection (blood and urine) (Section 6.16)
- Apply study drug to target treatment area¹ (Section 5.6)
- Dispense study drug supply and diary (Sections 6.18.1 and 6.18.2)

7.8 Visit 8 (Week 24 ± 5 days) – Early Termination – Site Visit

- Collect Patient/Observer-reported scales (Section 6.11)
- Collect study drug supply and diary (Sections 6.18.1 and 6.18.2)
- Record concomitant medications and adverse events (Sections 6.4 and 6.5)
- Collect urine sample for urinalysis and pregnancy test, if applicable (Sections 6.15.1.3 and 6.15.1.4)
- 12-lead ECG (Section 6.6)

¹ If treatment area will be expanded up to 90% BSA, Investigator should apply study drug to this expanded treatment area during the visit but after the collection of pre-dose PK samples.

- Collect vital signs (Section 6.7)
- Symptom-directed physical exam (Section 6.8)
- Complete dermatologic examination (Section 6.12)
- Take digital photography (Section 6.13)
- Complete VIIS (Section 6.9)
- Complete Global Impression of Severity (Section 6.10)
- PD sample collection (Section 6.14)
- Collect blood samples for hematology and chemistry (Sections 6.15.1.1 and 6.15.1.2)
- PK sample collection (blood and urine) (Section 6.16)

7.9 Visits 9 (Week 28 ± 3 days) – Safety Follow-up - Home Visit (Section 6.19)

- Record concomitant medications and adverse events (Sections 6.4 and 6.5)
- Complete dermatologic examination (Section 6.12)
- Take digital photography (Section 6.13)

8 STUDY ACTIVITIES FOR PART 2

Study activities for Part 2 are summarized in the Study Activities Schedule (Table 2).

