8.8 Visit 7 (Week 20 ± 3 days) – Telephone Check-In (Section 6.20)

• Record concomitant medications and adverse events (Sections 6.4 and 6.5)

8.9 Visit 8 (Week 24 ± 5 days) – Early Termination – Site Visit

- Collect Patient/Observer-reported scales (Section 6.11)
- Record concomitant medications and adverse events (Sections 6.4 and 6.5)
- Collect urine sample for urinalysis and pregnancy test, if applicable (Sections 6.15.1.3 and 6.15.1.4)
- 12-lead ECG and Holter monitoring (Section 6.6)
- Collect vital signs (Section 6.7)
- Symptom-directed physical exam (Section 6.8)
- Complete dermatologic examination (Section 6.12)
- Take digital photography (Section 6.13)
- Complete VIIS (Section 6.9)
- Complete clinician-reported global impression of severity scale (Section 6.10)
- PD sample collection (Section 6.14)
- Collect blood samples for hematology and chemistry (Sections 6.15.1.1 and 6.15.1.2)
- PK sample collection (blood and urine) (Section 6.16)
- Collect study drug supply and diary (Sections 6.18.1 and 6.18.2)
- Conduct Subject Exit Interview¹ (Section 6.21)

8.10 Visit 9 (Week 28 ± 5 days) – Safety Follow-up – Site Visit

- Collect Patient/Observer-reported scales (Section 6.11)
- Record concomitant medications and adverse events (Sections 6.4 and 6.5)
- Complete dermatologic examination (Section 6.12)
- Take digital photography (Section 6.13)

¹ Subject Exit Interview should be conducted within 30 days of the scheduled visit.

- Complete VIIS (Section 6.9)
- Complete Global Impression of Severity (Section 6.10)

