4. STUDY PROCEDURES AND FLOWCHART

Table 4.1.1-Part 1 Schedule of Events

	Screening ¹	Baseline Visit 1	Visit 2	Visit 3	Visit 4	Visit 5	Visit 6	Visit 7	ET Visit 8 ²	Safety Follow- Up Visit 9
Evaluation	Day -7 to -1	Week 1 Day 1	Week 1 Day 2	Week 4 ± 3 days	Week 8 ± 3 days	Week 12 ± 5 days	Week 16 ± 3 days	Week 20 ± 5 days	Week 24 ± 5 days	Week 28 ± 3 days
Evaluation	Site Visit	Site Visit	Site Visit	Home Visit	Home Visit	Site Visit	Home Visit	Site Visit	Site Visit	Home Visit
Informed consent / assent	Х									
Eligibility review	Х	X								
Demographics / medical history	Х									
Concomitant medications	Х	Х	X	Х	Х	Х	Х	Х	Х	Х
Adverse events	Х	X	Х	Х	Х	Х	Х	Х	Х	Х
Urinalysis/ urine pregnancy test ³	Х	Х				Х		Х	Х	
12-Lead ECG	Х	Х				Х		Х	Х	
Vital Signs	Х	Х	Х			Х		Х	Х	
Physical exam ⁴	Х	Х	Х			Х		Х	Х	
Dermatologic exam	Х	Х	Х	Х	Х	Х	Х	Х	Х	Х
Digital photography ⁵		Х		X ⁶	X ⁶	Х	X ⁶	Х	Х	X ⁶
VIIS (Investigator- assessed)		Х	Х			Х		Х	Х	
Global impression of severity		Х				Х		Х	Х	
Patient/Observer- reported scales ⁷		Х				Х		Х	Х	
PD sample collection ⁸		Х				Х		Х	Х	
Clinical laboratory testing ⁹	х	Х		Х		Х		Х	Х	
PK sample collection ¹⁰		Х	Х			Х		Х	Х	
Randomization		Х								
Administer study drug		X ¹¹	Х	Х	Х	X ¹¹	Х	X ¹¹	Х	
Dispense study drug & diary			Х			Х		Х		

Syneos Health #1009367

diary

ET = early termination; ECG = electrocardiogram; PD = pharmacodynamic; PK = pharmacokinetic; VIIS = Visual Index for Ichthyosis Severity

- 1. Samples collected for urinalysis and clinical laboratory tests may be analyzed at a local lab.
- 2. Subjects who terminate early from the study will not require post-dose assessments at Visit 8 (Week 24).
- 3. Urine pregnancy test for female subjects of child-bearing potential only. Test can be analyzed at the study site.
- 4. Complete physical exam, including height and weight collection, performed at Screening Visit only; symptom-directed physical exams at all other timepoints.
- 5. Subjects should refrain from bathing and applying study drug or as-needed topical symptom control therapy (emollients) to the treatment area within 12 hours of obtaining digital photographs.
- 6. During at-home visits, photographs will only be taken if there are any safety concerns.

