6.3. PHARMACOKINETIC ENDPOINTS

Full pharmacokinetic (PK) profile on Day 1 and at steady state following treatment up to 90% BSA. Planned analysis detailed in separate PK analysis plan.

Syneos Health #1009367

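### The documents disagree on whether study drug is applied at Visit 8, so the dose that anchors the post-dose PK, ECG and vital-sign times there is not ensured

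*Protocol*

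**What the plan says.** Texts that presuppose or allow a dose at Visit 8:

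- Protocol Table 1-1 has one block of columns for "Visits 5, 7 and 8", with a pre-dose reading and then 1, 2, 4 and 8 h for those aged 12 or over, or 1 and 4 h for younger children. Table 2-1 does the same for Part 2 Visits 4 and 8 and adds a 12 h point for the older group. Section 6.16 refers to these two tables for PK times, and Section 6.6 does so for ECG times.
- Footnote 11 to protocol Table 1: "At study visits when PK samples are collected, study drug may be administered at the study clinic after pre-dose PK samples have been obtained". The Part 2 footnote 11 is to the same effect.
- SAP "Table 4.1.1-Part 1 Schedule of Events" marks administration at Visit 8. Its footnote 2 excuses only early terminators from the post-dose assessments at that visit.
- SAP Section 6.3 gives the PK endpoint: "Full pharmacokinetic (PK) profile on Day 1 and at steady state following treatment up to 90% BSA".

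Texts that schedule no dose at Visit 8:

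- The row "Administer study drug" in protocol Table 1 is marked at Visits 1 to 7 and blank at Visit 8. Table 2 shows the same.
- Section 7.8 includes "PK sample collection (blood and urine) (Section 6.16") but no application step, whereas Sections 7.2, 7.3, 7.5 and 7.7 each have one. Section 8.9 includes "12-lead ECG and Holter monitoring (Section 6.6") and again no application step, whereas Section 8.5 (Part 2 Visit 4) has one.

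**The concern.** A post-dose time means something only if a dose was given at a known time just before it. A site working from Table 1 and Section 7.8 would apply nothing at Visit 8. If it then filled in the Table 1-1 grid, it would record the tail of the previous application under labels that say 1 to 8 h after dosing. A site working from Table 1-1 and footnote 11 would dose first. With about 9 subjects in Part 1, a mixture of the two under the same labels could not be averaged out.

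The stakes are highest in Part 1, where the treated area grows in steps and Visit 8 is the one profile taken after repeated whole-body application. Phase 2 treated only about 3% BSA (Section 1.4). The data safety monitoring board reviews Part 1 after about 9 subjects complete Week 24, and ECG readings and vital signs are among its inputs (Section 3.4.1).

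**Working it through.** No power or alpha figure is involved. The check sets the schedules side by side and counts the readings that depend on a Visit 8 dose.

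**1. What each text says about Visit 8**

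| Text | Dose at Visit 8? |
|---|---|
| Protocol Tables 1-1 and 2-1 | presupposed (pre-dose and post-dose columns) |
| Protocol Tables 1 and 2, administration row | not marked |
| Protocol Sections 7.8 and 8.9 | no application step |
| Protocol footnote 11 (Parts 1 and 2) | permitted, not required |
| SAP Table 4.1.1 (Part 1 only) | marked |

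**2. Could a home dose serve?** No. Section 5.6 bars application to the treatment area within 12 h of a site examination. The grid also needs a pre-dose sample at the visit, so the anchoring dose has to follow arrival at the site.

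**3. Which Part 1 profile is unique?** Under Table 1 footnote 11, Visit 1 is the first application at about 20% BSA, Visit 5 the first at up to 45%, and Visit 7 the first at up to 90%, if the area is expanded. Whole-body treatment then runs from Week 21 through Week 24 (Sections 3.1 and 5.6). Visit 8 is nominally (24 − 20) × 7 = 28 days after Visit 7. With both ±5-day windows the gap is 28 ± 10, or 18 to 38 days. Visit 8 is thus the only scheduled Part 1 profile after repeated application at up to 90% BSA.

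**4. Readings per subject at Visit 8 that need a dose** (ECG + vital signs + blood PK + urine PK)

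| | Aged 12 or over | Under 12 |
|---|---|---|
| Part 1 (Table 1-1) | 4 + 4 + 4 + 1 = 13 | 2 + 2 + 2 + 1 = 7 |
| Part 2 (Table 2-1), PK subjects | 5 + 5 + 5 + 1 = 16 | 2 + 2 + 2 + 1 = 7 |

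For about 9 Part 1 subjects this is between 9 × 7 = 63 and 9 × 13 = 117 readings. The age mix is not given. In Part 2, PK is taken from about 16 subjects. Subjects outside that group have only the timed ECGs and vital signs: 5 + 5 = 10 if aged 12 or over, and 2 + 2 = 4 if younger.

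**5. Is there another repeated-dose whole-body profile?** Yes, in Part 2. All affected areas are treated from Day 1. Visit 4 (Week 8) has the full grid in Table 2-1, an administration mark in Table 2 and an application step in Section 8.5, and these agree.

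**6. Early terminators.** Protocol Table 1 footnote 2 asks for all Visit 8 assessments where possible. SAP Table 4.1.1 footnote 2 drops the post-dose ones. These differ too.

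**The case against.** The strongest reply is that nothing forbids a Visit 8 dose. Footnote 11 covers visits with PK sampling, and Visit 8 is one. Its marker in Table 1 sits only on Visits 1, 5 and 7, but its text also instructs on Visit 2, which carries no marker, so marker placement does not bound its scope. In Part 2 the marker is on the row label. The administration row is also marked at home visits and telephone contacts, so it seems to track the daily dosing period, and the Visit 8 blank may mean only that the period ends there. A site that reads Table 1-1 alongside footnote 11 could well dose.

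That reply has force. A reader might infer that the steady-state profile at the largest treated area cannot be obtained as written. The documents do not support this: footnote 11 allows a clinic dose, the SAP schedule shows one, and Part 2 Visit 4 supplies a consistent repeated-dose whole-body profile. A reader might also count the 12-hour Holter recording at Part 2 Visit 8 as lost. Section 6.6 ties it to a visit, not to a dose.

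Two further points are fair. The PK and ECG analysis plans and the Laboratory and Pharmacy Manuals are separate documents not seen here and may settle the matter. And the SAP schedule differs from protocol Table 1 in other rows (PD sampling at Visit 2, laboratory tests at Visit 3), so it may not match this protocol text.

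What remains is that permission is not a requirement. Footnote 11 gives specific instructions for Visits 1, 2, 5 and 7 and none for Visit 8. The protocol's own conflict between Table 1 with Section 7.8 and Table 1-1 does not depend on the SAP. The SAP does not resolve it either: its Section 2 gives it precedence on analysis methods, not on study procedures, and its Section 13 does not list this difference.

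**Conclusion.** The documents contradict themselves on administration at Visit 8, and a dose to anchor the post-dose readings is not ensured.

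- **Part 1:** the only scheduled profile after repeated application at up to 90% BSA, which the SAP Section 6.3 endpoint needs, is at risk. The points affected are 1, 2, 4 and 8 h for those aged 12 or over (13 readings per subject) and 1 and 4 h for younger children (7 readings). The pre-dose readings at Visit 8 and the first-application profile at Visit 7 stay usable.
- **Part 2:** the risk is limited to the end-of-treatment post-dose points: PK in about 16 subjects, and the timed ECGs and vital signs.

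This rests on three assumptions. The unseen manuals and plans do not already specify Visit 8. Whole-body treatment in Part 1 starts at Visit 7 and runs from Week 21, as in Sections 3.1 and 5.6; the Synopsis gives Week 24 for that step, which also needs reconciling. Steady state is the SAP's own term and is not tested here. The inconsistency should be corrected, since it bears on a named endpoint and on safety data at the highest exposure.

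**What to change.** Reconcile protocol Tables 1, 1-1, 2 and 2-1, Sections 7.8 and 8.9, and SAP Table 4.1.1 so that all state the same thing about administration at Visit 8 and the timed assessments match it. If the outcome changes which readings exist at Visit 8, SAP Section 6.3 should be checked against it. Reconcile footnote 2 of protocol Table 1 and of SAP Table 4.1.1 on what early terminators undergo at Visit 8. Which schedule is right is for the sponsor to decide.

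For Part 1 subjects already seen, the PK and ECG analyses can use the recorded time since last application, where the diary or site record gives it, in place of the nominal label.

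The cost is schedule wording in two documents. No new visit is needed.
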